7.3.3 Medical History

A by-subject listing of general medical history for all randomized subjects will be provided.

7.3.4 Prior Therapy Agents

Prior therapy will be summarized for the relevant populations based on all randomized subjects.

Prior anti-cancer therapy:

- Setting of prior systemic therapy regimen received (adjuvant, metastatic disease, neo-adjuvant)
- Time from completion of prior adjuvant/neo-adjuvant therapy to treatment (for subjects who received prior adjuvant/neo-adjuvant therapy), (< 6 months, 6 -< 12month, ≥ 12 months)

- Prior surgery related to current cancer (yes or no)
- Prior radiotherapy (yes or no)
- Prior systemic therapy classified by therapeutic class and generic name

Other Prior therapy:

- Prior/current non-study medication classified by anatomic and therapeutic classes
- Agents and medication will be reported using the generic name. A listing by subject will also be provided.

7.3.5 Physical Examinations

Subjects with abnormal baseline physical examination will be listed by subject.

7.3.6 Baseline Physical Measurements

Baseline physical measurements will be listed by subject.

7.4 Extent of Exposure

Listings will include all available exposure data. Analyses will be performed on the relevant populations by treatment group “as treated” in all treated subjects, unless otherwise specified.

7.4.1 Administration of Study Therapy

The following parameters will be summarized (descriptive statistics) by treatment group. These analyses will be performed on the All Treated LAG-3 Positive Subjects, All Treated LAG-3 Negative Subjects, and All Treated Subjects.

- Relative dose intensity (%) using the following categories: < 50%; 50 - < 70%; 70 - < 90%; 90 - < 110%; ≥ 110%
- Number of doses/cycles received (summary statistics)
- Cumulative dose
- Duration of treatment
 - using a KM curve whereby the last dose date will be the event date for those subjects who are off study therapy. Subjects who are still on study therapy will be censored on their last dose date. Median duration of treatment and associated 95% CI will be provided.

A by-subject listing of dosing of study medication (record of study medication, infusion details, dose change) and a listing of batch number will be also provided.

Key parameters used to characterize dosing data are found in [Table 7.4.1-1](#), [7.4.1-2](#), and [7.4.1-3](#).

Table 7.4.1-1: Administration of Study Therapy for Subjects Treated with XELOX

	BMS-986213 or Nivolumab	Oxaliplatin	Capecitabine
Dosing schedule per protocol	Rela 120mg + Nivo 360mg (BMS-986213) Q3WK, IV or Nivo 360mg Q3WK, IV	130mg/m ² Q3WK, IV	1000mg/m ² Q3WK, oral
Dose*	Dose is defined as Total Dose administered (mg). Dose administered in mg at each dosing date are collected on the CRF	Total dose administered (mg) / most recent BSA	Total dose administered (mg) / most recent BSA
Cumulative Dose	The sum of all doses (mg) administered to a subject during the treatment period	The sum of all doses (mg/m ²) administered to a subject during the treatment period	The sum of all doses (mg/m ²) administered to a subject during the treatment period
Relative Dose Intensity (%)	Cumulative dose (mg) / [Last rela dose date – rela Start dose date + 21] x 120/21] Cumulative dose (mg) / [Last nivolumab dose date – nivolumab Start dose date + 21] x 360/21]	Cumulative dose (mg/m ²) / [Last oxaliplatin dose date – oxaliplatin Start dose date + 21] x 130/21]	Cumulative dose (mg/m ²) / [First dose of capecitabine in the last cycle – capecitabine Start dose date + 21] x 2000/21]
Duration of Treatment	Last dose date (of the last administered study therapy) - Start dose date (of the first administered study therapy) + 1		

* Dose administered in mg at each dosing date and BSA (computed using recent weight and baseline height) are collected on the CRF.

Table 7.4.1-2: Administration of Study Therapy for Subjects Treated with FOLFOX

	BMS-986213 or Nivolumab	Oxaliplatin	Leucovorin	Fluorouracil
Dosing schedule per protocol	Rela 160mg + Nivo 480mg (BMS-986213) Q4WK, IV or Nivo 480mg Q4WK, IV	85mg/m2 Q2WK	400mg/m2 Q2WK	Bolus 5-FU: 400mg/m2 Q2WK, IV on Day 1 of the cycle Continuous 5-FU: 1200mg/m2 Q2WK, IV continuous infusion on Day1-2 of the cycle
Dose*	Dose is defined as Total Dose administered (mg). Dose administered in mg at each dosing date are collected on the CRF	Total dose administered (mg) / most recent BSA	Total dose administered (mg) / most recent BSA	Total dose administered (mg) / most recent BSA
Cumulative Dose	The sum of all doses (mg) administered to a subject during the treatment period	The sum of all doses (mg/m2) administered to a subject during the treatment period	The sum of all doses (mg/m2) administered to a subject during the treatment period	The sum of all doses (mg/m2) administered to a subject during the treatment period
Relative Dose Intensity (%)	Cumulative dose (mg) / [Last rela dose date – rela Start dose date + 28) x 160/28] Cumulative dose (mg) / [Last nivolumab dose date – nivolumab Start dose date + 28) x 480/28]	Cumulative dose (mg/m2) / [Last oxaliplatin dose date – oxaliplatin Start dose date + 14) x 85/14]	Cumulative dose (mg/m2) / [Last leucovorin dose date – leucovorin Start dose date + 14) x 400/14]	Bolus 5-FU: Cumulative dose (mg/m2) / [First dose of fluorouracil in the last cycle – fluorouracil Start dose date + 14) x 400/14] Continuous 5-FU: Cumulative dose (mg/m2) / [First dose of continuous fluorouracil in the last cycle – continuous fluorouracil Start dose date + 14) x 1200/14]
Duration of Treatment	Last dose date (of the last administered study therapy) - Start dose date (of the first administered study therapy) + 1			

* Dose administered in mg at each dosing date and BSA (computed using recent weight and baseline height) are collected on the CRF.

Table 7.4.1-3: Administration of Study Therapy for Subjects Treated with SOX

	BMS-986213 or Nivolumab	Oxaliplatin	S-1 (tegafur/gimeracil/oteracil)
Dosing schedule per protocol	Rela 120mg + Nivo 360mg (BMS-986213) Q3WK, IV or Nivo 360mg Q3WK, IV	130mg/m ² Q3WK, IV	S-1 (tegafur/gimeracil/oteracil) BID, oral (administered as calculated according to body surface area (BSA, mg/m ² /dose): BSA < 1.25 m ² , 40 mg/dose; ≥1.25 and < 1.5 m ² , 50 mg/dose; ≥1.5 m ² , 60 mg/dose)
Dose*	Dose is defined as Total Dose administered (mg). Dose administered in mg at each dosing date are collected on the CRF	Total dose administered (mg) / most recent BSA	Total dose administered (mg) / most recent BSA
Cumulative Dose	The sum of all doses (mg) administered to a subject during the treatment period	The sum of all doses (mg/m ²) administered to a subject during the treatment period	The sum of all doses (mg/m ²) administered to a subject during the treatment period
Relative Dose Intensity (%)	Cumulative dose (mg) / [Last rela dose date – rela Start dose date + 21] x 120/21] Cumulative dose (mg) / [Last nivolumab dose date – nivolumab Start dose date + 21] x 360/21]	Cumulative dose (mg/m ²) / [Last oxaliplatin dose date – oxaliplatin Start dose date + 21] x 130/21]	BSA <1.25m ² : Cumulative dose (mg/m ²) / [First dose of S-1 in the last cycle – S-1 Start dose date + 14) x 1,120/14] BSA ≥1.25 and < 1.5 m ² : Cumulative dose (mg/m ²) / [First dose of S-1 in the last cycle – S-1 Start dose date + 14) x 1,400/14] BSA ≥1.5 m ² : Cumulative dose (mg/m ²) / [First dose of S-1 in the last cycle – S-1 Start dose date + 14) x 1,680/14]
Duration of Treatment	Last dose date (of the last administered study therapy) - Start dose date (of the first administered study therapy) + 1		

* Dose administered in mg at each dosing date and BSA (computed using recent weight and baseline height) are collected on the CRF.

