7.4.2 Modifications of Study Therapy

7.4.2.1 Dose Delays

Table 7.4.2.1-1: Dose Delays

	Q4W BMS-986213 or Nivolumab	Q3W BMS-986213 or Nivolumab	XELOX	FOLFOX	SOX
Specifications per Protocol					
Dose considered as actually delayed	If the delay is exceeding 3 days	If the delay is exceeding 3 days	Per package insert or local standard	Per package insert or local standard	Per package insert or local standard
Maximum delay allowed between doses	42 days	42 days	Not specified	Not specified	Not specified
Definitions for the Analysis					
Dose Delay	duration of preceding cycle in days – 28	duration of preceding cycle in days – 21	duration of preceding cycle in days – 21	duration of preceding cycle in days – 14	duration of preceding cycle in days – 14
Categories of dose delays	on-time, 4 - 7 days, 8 - 14 days, 15 - 42 days, > 42 days	on-time, 4 - 7 days, 8 - 14 days, 15 - 42 days, > 42 days	on-time, 4 - 7 days, 8 - 14 days, 15 - 42 days, > 42 days	on-time, 3 - 4, 5 - 7 days, 8 - 14 days, 15 - 42 days, > 42 days	on-time, 4 - 7 days, 8 - 14 days, 15 - 42 days, > 42 days

The following parameters will be summarized by treatment arm:

- Number of dose delayed per subject, Length of Delay and Reason for Dose Delay

Reason for dose delay will be retrieved from CRF dosing pages.

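### Three relative dose intensity formulas and the SOX delay formula in the SAP do not match the protocol schedule: full adherence scores 1400%, 200% or at most 80%, and on-time SOX doses score 7 days late

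*SAP*

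**What the plan says.** SAP section 7.4.1 defines relative dose intensity (RDI) as cumulative dose over the planned dose for the time on drug. It reports RDI in five bands, the lowest below 50% and the highest 110% or more, for all treated subjects and for each LAG-3 group. Cumulative dose adds up every dose given during treatment, and the table footnote says: "Dose administered in mg at each dosing date and BSA (computed using recent weight and baseline height) are collected on the CRF".

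The rows in question are:

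- **Capecitabine (Table 7.4.1-1):** the denominator ends "capecitabine Start dose date + 21] x 2000/21". The schedule cell gives 1000 mg/m² every 3 weeks by mouth, with no mention of twice-daily dosing or of 14 days on treatment.
- **Infusional fluorouracil (Table 7.4.1-2):** the denominator ends "continuous fluorouracil Start dose date + 14) x 1200/14", although the schedule cell describes "IV continuous infusion on Day1-2 of the cycle".
- **S-1 (Table 7.4.1-3):** in the lowest body surface area (BSA) band the denominator ends "S-1 Start dose date + 14) x 1,120/14". The other bands use 1,400 and 1,680. The numerator is divided by BSA.
- **SOX delay (Table 7.4.2.1-1):** the SOX column uses "duration of preceding cycle in days – 14", the same as FOLFOX. XELOX subtracts 21.

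The protocol (sections 7.1.2 to 7.1.4) gives capecitabine and S-1 twice daily for 14 days in each 21. It gives infusional fluorouracil at 1200 mg/m² on each of two days every 14 days. SOX is a 3-week regimen in the notes to protocol Figure 5.1-1.

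**The concern.** RDI should be 100% when a patient takes exactly what was planned. That needs a numerator and a denominator that count the same doses, in the same units, over the same interval. Here the capecitabine denominator holds one day's dose and the infusional fluorouracil denominator one of two infusion days. The S-1 denominator spreads a course over 14 days when it repeats every 21, and sets mg/m² against flat mg. The SOX delay row uses a 2-week interval for a 3-week regimen.

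At stake is whether the exposure tables can be read at all. Safety is a secondary objective, and how much chemotherapy each arm received is part of interpreting it. If nearly every capecitabine patient falls in the top RDI band, the table says nothing about reductions. If every on-time SOX dose falls in a delay band, the delay table gives a false picture of that regimen.

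**Working it through.** **Readings used.** (i) A cycle in these tables is the drug's dosing interval. The SAP supports this: a 2-weekly drug is placed on days of the cycle, and the Q4W immunotherapy delay is "duration of preceding cycle in days – 28". (ii) Every dose is summed, as the cumulative dose row says. Let n be the number of completed on-time intervals at full dose.

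**The SAP constants.**
- Capecitabine: 2000 = 2 × 1000, one day.
- Infusional fluorouracil: 1200 = one infusion day.
- S-1: 1,120 = 40 × 28; 1,400 = 50 × 28; 1,680 = 60 × 28. These are 14-day course totals in mg.

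**Control rows.** With dose d every k days, RDI = dn / [(k(n − 1) + k) × d/k] = 100% for any n. Relatlimab, nivolumab, oxaliplatin, leucovorin and bolus fluorouracil all meet this, so the reading fits the rest of the tables.

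**Capecitabine.** Protocol amount per 21 days: 1000 × 2 × 14 = 28,000 mg/m².
- RDI = 28,000n / (21n × 2000/21) = 14 = 1400%.
- On-time dosing at 75% or 50% of the starting dose: 1050% or 700%.
- The top band is reached at 1.1/14 = 7.9% of plan.

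**Infusional fluorouracil.** Protocol amount per 14 days: 1200 × 2 = 2400 mg/m², which protocol Table 7.3.3.3-1 also states per 48 hours.
- RDI = 2400n / (14n × 1200/14) = 200%.
- Dose level −1: 2000/1200 = 167%. Dose level −2: 1600/1200 = 133%.
- The top band is reached at 1.1/2 = 55% of plan.

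**S-1.** With course total D mg, RDI = (Dn/BSA) / [(21(n − 1) + 14) × D/14] = 2n / [(3n − 1) × BSA].

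| Courses n | BSA 1.25 m² | BSA 1.5 m² |
|---|---|---|
| 1 | 80% | 66.7% |
| 2 | 64% | 53.3% |
| 6 | 56.5% | 47.1% |

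Two faults act together. Even in mg, the 14-day constant takes RDI from 100% at n = 1 towards 66.7%. Dividing by BSA then lowers it again wherever BSA exceeds 1 m².

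**SOX delay.** An on-time dose scores 21 − 14 = 7 days, in the 4 to 7 day band. On-time XELOX scores 21 − 21 = 0.

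**If a cycle meant 6 weeks** (protocol 5.1.2, SAP 2.1), the rows would still be wrong:

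| Row | Formula | 1 cycle | 2 cycles | 4 cycles |
|---|---|---|---|---|
| Capecitabine | 28n/(2n − 1) | 2800% | 1867% | 1600% |
| Infusional fluorouracil | 6n/(3n − 2) | 600% | 300% | 240% |
| Bolus fluorouracil | 3n/(3n − 2) | 300% | 150% | 120% |
| S-1, BSA 1.25 m² | 2n/[(3n − 2) × BSA] | 160% | 80% | 64% |

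On-time doses would also score late in every delay column: 42 − 14 = 28 days for SOX and FOLFOX, 42 − 21 = 21 for XELOX and Q3W immunotherapy, and 42 − 28 = 14 for Q4W immunotherapy.

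**The case against.** The strongest reply is that the case report form is not available. If it records one daily dose per course for capecitabine and for infusional fluorouracil, both rows return 100% (2000/2000 and 1200/1200), and S-1 could be recorded differently. So the 1400% and 200% figures are conditional. That stands as a caution, but this convention conflicts with a cumulative dose that adds every dose and a footnote that collects doses at each dosing date. Applied to S-1 as well, it gives 80/1,120, about 7% before dividing by BSA. No recording convention mends the SOX delay row.

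Other points that stand:

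- The 80% ceiling for S-1 assumes the most recent BSA stays at or above 1.25 m². At a BSA of 1.0 m² and n = 1 the formula gives 100%.
- Tablet rounding, changes in BSA and local infusion practice will move individual values, so 100% after correction holds for nominal dosing.
- Reductions remain visible elsewhere. Cumulative dose and number of doses are summarized, SAP section 7.6.4 tabulates adverse events leading to delay or reduction, and section 7.4.1 plans "A by-subject listing of dosing of study medication (record of study medication, infusion details, dose change" and related records.
- Both arms use the same formulas, and no endpoint or decision rule uses RDI or delay.

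These points limit the consequence. They do not make the formulas correct.

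**Conclusion.** The concern holds. Four exposure rows in the SAP disagree with the protocol schedule, and programmed as written they would produce wrong tables. On the dosing-interval reading with every dose summed, full adherence gives 1400% for capecitabine, 200% for infusional fluorouracil and at most 80% for S-1 at a BSA of 1.25 m² or more, and each on-time SOX dose scores 7 days late. The 6-week reading changes the sizes and puts further rows in error.

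The mismatches do not depend on assumptions; the percentages depend on the two readings and on the unseen recording convention. The effect is confined to the descriptive RDI and dose-delay tables, and the response analysis is untouched. The documents do not say how many patients receive SOX, so the reach of the S-1 and SOX delay errors is unknown. This should be corrected before the exposure tables are programmed or reported.

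**What to change.** Bring the SAP reporting formulas into line with the schedule the protocol states. This changes how exposure is reported, not any dose.

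- **Footnote on Tables 7.4.1-1 to 7.4.1-3 and 7.4.2.1-1:** a cycle means the drug's dosing interval (28 days for Q4W immunotherapy; 21 for Q3W immunotherapy, XELOX and SOX; 14 for FOLFOX), not the 6-week study cycle.
- **Capecitabine:** use 28,000/21, and make the schedule cell agree with the protocol's twice-daily, 14-of-21-day schedule.
- **Infusional fluorouracil:** use 2400/14, with a note for sites that follow local infusion practice.
- **S-1:** use + 21 with 1,120/21, 1,400/21 and 1,680/21, and state dose and cumulative dose in mg, not divided by BSA.
- **SOX delay:** subtract 21.

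Check at nominal full adherence: 28,000n/(21n × 28,000/21) = 1; 2400n/(14n × 2400/14) = 1; Dn/(21n × D/21) = 1; SOX delay 21 − 21 = 0.

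The cost is seven table cells (capecitabine schedule and RDI, infusional fluorouracil RDI, S-1 dose, cumulative dose and RDI, and SOX delay), one footnote on four tables, and the matching programs. No new data are needed.

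Separately, Table 7.4.2.1-1 gives 42 days as the maximum delay for Q4W immunotherapy, while protocol section 7.3.7 sets its limit with FOLFOX at more than 8 weeks from the previous dose. The two passages must be reconciled.

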7.4.2 Modifications of Study Therapy

7.4.2.1 Dose Delays

Table 7.4.2.1-1: Dose Delays

	Q4W BMS-986213 or Nivolumab	Q3W BMS-986213 or Nivolumab	XELOX	FOLFOX	SOX
Specifications per Protocol					
Dose considered as actually delayed	If the delay is exceeding 3 days	If the delay is exceeding 3 days	Per package insert or local standard	Per package insert or local standard	Per package insert or local standard
Maximum delay allowed between doses	42 days	42 days	Not specified	Not specified	Not specified
Definitions for the Analysis					
Dose Delay	duration of preceding cycle in days – 28	duration of preceding cycle in days – 21	duration of preceding cycle in days – 21	duration of preceding cycle in days – 14	duration of preceding cycle in days – 14
Categories of dose delays	on-time, 4 - 7 days, 8 - 14 days, 15 - 42 days, > 42 days	on-time, 4 - 7 days, 8 - 14 days, 15 - 42 days, > 42 days	on-time, 4 - 7 days, 8 - 14 days, 15 - 42 days, > 42 days	on-time, 3 - 4, 5 - 7 days, 8 - 14 days, 15 - 42 days, > 42 days	on-time, 4 - 7 days, 8 - 14 days, 15 - 42 days, > 42 days

The following parameters will be summarized by treatment arm:

- Number of dose delayed per subject, Length of Delay and Reason for Dose Delay

Reason for dose delay will be retrieved from CRF dosing pages.

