 - Grade 4 drug-related endocrinopathy AEs, such as, hyper- or hypothyroidism, or glucose intolerance, which resolve or are adequately controlled with physiologic hormone replacement (corticosteroids, thyroid hormones) or glucose-controlling agents, respectively, may not require discontinuation after discussion with and approval from the BMS Medical Monitor
 - Any event that leads to delay in dosing lasting > 8 weeks in the BMS-986213 or nivolumab PLUS FOLFOX treatment (or > 6 weeks in the BMS-986213 or nivolumab PLUS either XELOX or SOX treatment) from the previous dose requires discontinuation, with the following exceptions:
 - Dosing delays to allow for prolonged steroid tapers to manage drug-related AEs are allowed.
 - Dosing delays lasting > 8 weeks in the BMS-986213 or nivolumab PLUS FOLFOX treatment (or > 6 weeks in the BMS-986213 or nivolumab PLUS either XELOX or SOX treatment) from the previous dose that occur for non-drug-related reasons may be allowed if approved by the BMS medical monitor.
 - Any AE, laboratory abnormality, or intercurrent illness that, in the judgment of the Investigator, presents a substantial clinical risk to the participant with continued BMS-986213 or nivolumab dosing.

Prior to reinitiating treatment in a participant with a dosing delay lasting > 8 weeks in the BMS-986213 or nivolumab PLUS FOLFOX treatment (or > 6 weeks in the BMS-986213 or nivolumab PLUS either XELOX or SOX treatment) from the previous dose, the BMS Medical Monitor must be consulted. Tumor assessments should continue as per protocol even if dosing is delayed.

Periodic study visits to assess safety and laboratory studies should also continue every 6 weeks or more frequently if clinically indicated during such dosing delays.

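### SAP dose-delay table gives 42 days where the protocol allows 8 weeks for Q4W immunotherapy, and measures three-weekly SOX against a 14-day interval

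*SAP*

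**What the plan says.** SAP 7.4.2.1 plans a by-arm summary of the "Number of dose delayed per subject, Length of Delay and Reason for Dose Delay", built on Table 7.4.2.1-1. The table has two blocks.

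- **Specifications per protocol.** The row "Maximum delay allowed between doses" gives 42 days for Q4W immunotherapy, 42 days for Q3W immunotherapy, and *Not specified* for XELOX, FOLFOX and SOX.
- **Definitions for the analysis.** Delay is "duration of preceding cycle in days – 28" for Q4W immunotherapy. The constant is 21 for Q3W immunotherapy and for XELOX. For FOLFOX and SOX the definition is "duration of preceding cycle in days – 14". The categories for both immunotherapy schedules, XELOX and SOX are "on-time, 4 - 7 days, 8 - 14 days, 15 - 42 days, > 42 days". FOLFOX has a finer lower end.

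Protocol 7.3.7 sets the limit beyond which immunotherapy must stop, and the limit depends on the chemotherapy partner. For the four-weekly schedule the trigger is "Any event that leads to delay in dosing lasting > 8 weeks in the BMS-986213 or nivolumab PLUS FOLFOX treatment". For the three-weekly schedules the same sentence gives a shorter limit and names the point from which both are counted: "or > 6 weeks in the BMS-986213 or nivolumab PLUS either XELOX or SOX treatment) from the previous dose requires discontinuation". The section then lists exceptions, one of which reads: "Dosing delays to allow for prolonged steroid tapers to manage drug-related AEs are allowed".

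Protocol 7.1.4 gives SOX oxaliplatin on Days 1 and 22, and S-1 on Days 1 to 14 and 22 to 35, of each 6-week cycle.

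**The concern.** A block that claims to restate the protocol should agree with it, and the Q4W cell does not. A reader of the dose-delay table would take 42 days as the protocol's limit for patients on FOLFOX and could regard permitted intervals as excessive.

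The SOX constant matters more in practice, because it changes tabulated results. It turns punctual dosing into a recorded delay for every participant on that regimen. SAP section 8 sends all SAP analyses to the clinical study report unless otherwise noted, so both errors would be carried there.

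The *Not specified* entries are also inaccurate, because the protocol does limit how long a chemotherapy component may be held for toxicity.

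**Working it through.** **Assumption.** In the delay definitions, *preceding cycle* means the interval between consecutive doses. The protocol's own cycle is 6 weeks, and subtracting 28, 21 or 14 makes sense only on the dosing-interval reading.

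**1. Immunotherapy maximum.** Inputs: 8 weeks and 6 weeks from the previous dose (protocol 7.3.7), and 42 days in both cells (SAP Table 7.4.2.1-1).

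- Q3W: 6 × 7 = 42 days. The SAP figure is reproduced.
- Q4W: 8 × 7 = 56 days. The SAP figure is not reproduced, since 42 − 56 = −14 days.

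Other readings do not rescue the Q4W cell. On the SAP's delay scale the limit is 56 − 28 = 28 days, not 42. If 8 weeks were counted from the scheduled date instead, the maximum delay would be 56 days, again not 42.

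**2. SOX delay.** Inputs: dosing on Days 1 and 22 (protocol 7.1.4), and the constant 14 (SAP). The scheduled interval is 22 − 1 = 21 days.

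| Actual interval (days) | SAP delay (interval − 14) | SAP category | Delay on the 21-day schedule | Category on that schedule |
|---|---|---|---|---|
| 21 | 7 | 4 to 7 | 0 | on-time |
| 24 | 10 | 8 to 14 | 3 | on-time |
| 28 | 14 | 8 to 14 | 7 | 4 to 7 |
| 35 | 21 | 15 to 42 | 14 | 8 to 14 |

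The error is 21 − 14 = 7 days at every interval. Three points elsewhere indicate a slip:

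- XELOX, with capecitabine on the same Days 1 to 14 and 22 to 35, uses 21.
- SAP Table 7.4.1-3 lists SOX oxaliplatin as three-weekly with a 21-day denominator.
- The SOX categories match those of XELOX, not those of FOLFOX.

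**3. The same base in the S-1 relative dose intensity formulas.** SAP Table 7.4.1-3 adds 14 to the span from S-1 start to the first dose of the last cycle. It then multiplies by 1,120/14, 1,400/14 or 1,680/14 according to body surface area. The numerators are full dosing periods: 40 × 2 × 14 = 1,120, 50 × 2 × 14 = 1,400 and 60 × 2 × 14 = 1,680 mg. Each is planned once per 21 days.

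Take cumulative dose in mg and a 21-day period as the cycle. A participant with n full, punctual periods then has intensity

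1,120n / {[21(n − 1) + 14] × 80} = 2n/(3n − 1).

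This gives 100% at n = 1, 4/5 = 80% at n = 2 and 8/11 = 73% at n = 4, and it tends to 14/21 = 67%. With 21 in both places it is 100% for every n. The other two bands give the same ratio.

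**4. Chemotherapy maximum.**

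| Protocol section | Rule |
|---|---|
| 7.3.3.1 | Any component may be held up to 6 weeks for unresolved toxicity, then stops unless the investigator sees benefit in continuing |
| 7.3.4 | The same idea, as 42 days for toxicity to resolve |
| 7.3.3.2 (XELOX) | Oxaliplatin stops after 4 weeks skipped for neurologic toxicity |
| 7.3.3.3 (FOLFOX) | 4-week stops for neutropenia, diarrhea and (oxaliplatin only) neuropathy |

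SOX has only the general rules of 7.3.3.1 and 7.3.4.

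**The case against.** **The Q3W cell.** A reader might infer that it is wrong too, because 42 days would be too long if treated as a delay on the SAP's scale. The documents do not support that. The cell sits in the protocol-specification block, the protocol counts from the previous dose, and 42 days equals 6 weeks. Only its wording could be clearer.

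**The categories.** A reader might also infer that the 15-to-42-day category misstates the protocol because it has no cut at the discontinuation limits. The categories state no limit, and the SAP does not say that they monitor 7.3.7. Because that section permits steroid-taper delays and approved non-drug-related delays, a cut on length alone would not identify breaches. Finer categories are a preference, and the by-subject dosing listing in SAP 7.4.1 allows reconstruction.

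**Chemotherapy.** It is fair to say that the protocol has no single maximum per regimen. The limits depend on toxicity, some apply to oxaliplatin only, the 6-week rule yields to the investigator, and dosing windows follow the package insert or local standard. That argues for a cross-reference over a list of figures. It does not make *Not specified* accurate.

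**SOX.** The table separately leaves to the package insert or local standard whether a SOX dose counts as actually delayed, so an on-schedule dose might escape the count. This does not rescue the formula: the analysis definition and categories still apply the 14-day subtraction.

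It is also true that the SAP reports no enrollment from Japan or Taiwan and gives no count of SOX recipients. The visible text does not restrict SOX to those countries, so the group could be empty, small or larger.

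**Conclusion.** Two errors and one inaccurate entry stand. The Q4W maximum is 14 days too short against protocol 7.3.7 (42 against 56 days from the previous dose). The SOX delay is overstated by 7 days at every interval, so on-schedule doses are categorized as delayed. *Not specified* overlooks conditional limits that the protocol does give. The S-1 relative dose intensity formulas carry the same 14-day base and need checking. On the assumptions in the working, they would put a punctual, full-dose participant between 67% and 100%.

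Severity is minor. The tables are descriptive and the rules are the same in both arms. The objective response and progression-free survival analyses, the significance level and the sample size are untouched. A reader might infer that patients would be stopped at the wrong time, but treatment follows the protocol, whose limits are clear, and not this SAP table. The documents give no frequency of delays and no number on SOX, so no count of affected participants can be stated.

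**What to change.** Edit the SAP as follows.

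1. **Table 7.4.2.1-1, maximum row, Q4W:** 8 weeks (56 days) from the previous dose, exceptions per protocol 7.3.7.
2. **Same row, Q3W:** 6 weeks (42 days) from the previous dose. This is for clarity only, as the value does not change.
3. **Same row, XELOX, FOLFOX and SOX:** no single maximum; toxicity-conditional component limits per protocol 7.3.3.1 to 7.3.3.3 and 7.3.4 (general limit 6 weeks, investigator may override). A cross-reference is safer than a paraphrase. For example, the XELOX rule equates 4 weeks with two consecutive doses of a three-weekly drug, and the SAP should not have to interpret that.
4. **Same table, SOX delay:** subtract 21 instead of 14.
5. **Table 7.4.1-3, S-1 relative dose intensity:** check the three formulas and, unless there is a reason for the 14-day base, use 21 both as the added days and as the divisor.

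The cost is five cells, one constant and up to three formulas, with the matching programming. Dosing data and delay reasons are already taken from the CRF, so no protocol amendment, new data or site work is needed.
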